# 3 Study Enrollment and Withdrawal

# 5.1 Inclusion Criteria

In order to be eligible to participate in this study, an individual must meet all of the following criteria:

- 1. Males and females age 18-70
- 2. DSM-5 diagnosis of moderate or severe AUD

3. DSM-5 diagnosis of PTSD with Clinician Administered PTSD Scale (CAPS-5) OR subPTSD diagnosis (meeting criterion A, F, G, H and at least 6 symptoms across any criteria B-E) with Clinician Administered PTSD Scale (CAPS-5)

4. Able to provide voluntary informed consent

5. At least 4 heavy drinking days (4 or more drinks per day for a woman, 5 or more drinks per day for a man) in the 30 days prior to screen

6. If of childbearing potential (male or female), are willing to use approved form of contraception from screening for duration of the trial

- 7. Able to provide at least two locators
- 8. Endorse desire to cut down or stop drinking
- 9. Agrees to abstain from all other cannabinoid use for the duration of the study
- 10. Confirms they are reliably domiciled

# 5.2 Exclusion Criteria

An individual who meets any of the following criteria will be excluded from participation in this study:

1. Current alcohol withdrawal (CIWA-Ar score >7)

2. Exclusionary medical conditions (e.g. current severe alcohol withdrawal requiring medical hospitalization, significantly impaired liver function)

3. DSM-5 diagnosis of schizophrenia, schizoaffective disorder, bipolar disorder I

4. High risk of adverse emotional or behavioral reaction, and/or an inability to understand study procedures or the informed consent process, based on investigator's clinical evaluation (e.g., evidence of serious personality disorder, antisocial behavior, serious current stressors, lack of meaningful social support)

5. Exposure to trauma in the last 30 days, including police duty or military service

6. Current significant suicidality (assessed using the C-SSRS), any significant suicidal behavior in the past 12 months, or any history of serious suicide attempts requiring hospitalization, or current significant homicidality

7. History of Severe Traumatic Brain Injury (TBI; as indicated by Loss of Consciousness > 24 hours)

8. DSM-5 diagnosis of current mild cannabis use disorder and/or moderate or severe substance use disorder for a substance other than alcohol or nicotine

9. Significant laboratory abnormalities, including significantly impaired liver function, serious abnormalities of complete blood count or metabolic panel

10. Active legal problems likely to result in incarceration within 12 weeks of treatment initiation

11. Pregnancy or lactation

12. Current use of exclusionary medications, including cannabinoids; treatments for addictions including alcohol; moderate to strong inhibitors of CYP3A4 or CYP2C19; medications metabolized primarily by CYP3A5 or CYP3A7; and medications with a narrow therapeutic index which are substrates of CYP3A4, UGT1A9, UGT2B7, CYP2C8, CYP2C9, CYP2C19, CYP1A2, or CYP2B6.

13. Current treatment for AUD (with exceptions of: AA/12-step treatment and/or psychosocial treatment initiated more than 2 months prior to the screening visit)

14. Current treatment for methadone or opioid abuse

15. Psychotherapy for PTSD or other psychiatric condition, if initiated within 2 months of screening

16. Inpatient psychiatric treatment in the last 12 months, with the exception of detox and extended Emergency Department stays

17. A positive urine drug screen for opioids at screen, baseline, or any later visits. If a participant has a positive drug screen for THC or cocaine at screen, baseline or a later visit- their enrollment will be subject to the clinical judgement of the Principal Investigator. Please refer to the Medical and Psychiatric Safety SOP for further details.

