The proposed study is a double-blind, randomized proof-of-concept study designed to assess feasibility and contrast effects of CBD treatment to those of placebo on safety, drinking-related outcomes and PTSD/subthreshold PTSD related outcomes in patients with AUD+PTSD/subthreshold PTSD. We will evaluate the safety of an extended daily CBD treatment regimen in an AUD+PTSD/subthreshold PTSD population and measure resulting CBD, THC, and anandamide levels. We will also generate preliminary data on the impact of CBD on alcohol use, PTSD symptoms, a human laboratory traumatic stress induced craving task, neuropsychological and neurophysiological domains implicated in AUD and PTSD/subthreshold PTSD, and cognitive ability. Cannabidiol levels will be obtained from CBD-treated participants to estimate the plasma levels corresponding with putative therapeutic effects and to determine whether dose accumulation occurs. THC levels will be obtained from CBD-treated participants to determine whether CBD metabolites are converted into THC, as has been suggested in the literature [77]. Anandamide levels will be obtained from all participants to test whether CBD elevates plasma anandamide, and to provide preliminary data for relating anandamide levels to putative therapeutic effects. Following screening and baseline assessments, 48 participants will be randomized in a 5:3 ratio to receive either 600mg CBD/day (PO) or placebo respectively for 6 weeks (N=30 participants on CBD and N=18 participants on placebo). Safety measures (adverse events, cognitive and motoric function), drinking related outcomes and PTSD symptoms will be assessed weekly throughout the study. Human laboratory tasks, neuropsychological domains implicated in AUD and PTSD/subthreshold PTSD and cognition will be assessed at baseline and at the end of treatment. Measurement of circulating levels of Delta-9 THC, 11-Hydroxy Delta-9 THC and Delta-9 Carboxy THC will be obtained from CBD-treated participants only at baseline, 45 minutes, 1 day, 1 week, 2 weeks, 4 weeks, 6 weeks, and 7 weeks after treatment with the first dose of CBD vs. placebo. Anandamide levels will be obtained from both CBD- and placebo-treated participants at the aforementioned timepoints.

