## 5.7 Participant Withdrawal or Termination

#### 5.7.1 Reasons for Withdrawal or Termination

Participants are free to withdraw from participation in the study at any time upon request. An investigator may terminate participation in the study if:

• Any clinical adverse event (AE), laboratory abnormality, or other medical condition or situation occurs such that continued participation in the study would not be in the best interest of the participant

- The participant meets an exclusion criterion (either newly developed or not previously recognized) that precludes further study participation
- The participant fails to adhere to protocol requirements

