## 5.7.2 Handling of Participant Withdrawals or Termination

Every effort will be made to undertake the protocol-specified safety follow-up procedures to capture AEs, SAEs, and UPs. The investigator will attempt to obtain at a minimum safety/survival data on all participants lost to follow-up. If a participant is lost to follow-up, they study team will attempt to contact the participant up to 15 times by telephone, email, or text message. If the participant fails to respond, locators identified by the participant at screening will be contacted up to three times in the method specified by the participant. If participants withdraw, are terminated, or are lost to follow-up prior to the end of the 6-week treatment phase (prior to T8), they will not be replaced to maintain 48 randomized participants to complete the 6-week treatment phase (through T8) and their partial data will be handled according to the statistical analysis plan (SAP).

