PhenX Tier 1 measures and a Locator form will be completed at screening to collect contact information, demographics, BMI, quality of life, HIV risk and status, and substance use measures (age of onset, past 30-day quantity and frequency, lifetime use for alcohol, tobacco, and other substances; www.phenxtoolkit.org). The Clinical Institute Withdrawal Scale- Alcohol, revised (CIWA-Ar) will be used to verify lack of alcohol withdrawal [95], a urine drug screen (UDS) will be done at every in-person study visit (except for visits less than 24 hours from the last visit; i.e. 1 day visit) to verify lack of recent cannabinoid and other drug use, and a urine pregnancy test will be done at each in-person study visit (for women of childbearing potential: if female except those menopausal for >1 year since last menstrual period, had a hysterectomy, and/or had tubal ligation) to verify lack of pregnancy. If subjects are found to have suicidal intentions based on screening tests, appropriate referrals to mental health professionals will be made by the PI.

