## 15.4 Pregnancy Reporting

Pregnancy information on clinical study subjects is collected by the investigator. If a subject should become pregnant during the course of the study, the investigator or qualified designee will contact the IRB within 5 working days of the PI or qualified designee first becoming aware of the pregnancy.

Tilray Pregnancy Reporting Requirements: Every exposure during pregnancy (participant) should be reported on a Tilray SAE worksheet within 24 hours of the site becoming aware of the pregnancy as a case of special interest from the time of study enrollment to the end of study participation. If an SAE occurs in conjunction with the pregnancy, then the Tilray reporting timeframe for an SAE (24 hours) must be met. In the event of a pregnancy, administration of study medication will be discontinued, but all other follow-up data, including safety data, will be collected.

Pregnancies resulting in congenital abnormalities or birth defects in offspring meet the requirements for an SAE and will be collected, documented, and reported according to the procedures outlined above for SAEs.

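### Exclusion criterion 17 also operates after randomisation, and only safety follow-up is promised if participation then ends, so week-6 efficacy data may go uncollected for some randomised participants

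*Combined protocol and SAP*

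**What the plan says.** Criterion 17 is in Section 5.2, among the conditions that bar a person from the study. Its first sentence reads "A positive urine drug screen for opioids at screen, baseline, or any later visits". The next sentence reads, in part, "positive drug screen for THC or cocaine at screen, baseline or a later visit- their enrollment will be subject to the clinical judgement"; that judgement belongs to the Principal Investigator, and the criterion then refers to a Medical and Psychiatric Safety SOP for details.

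Under Section 7.1 the urine drug screen "will be done at every in-person study visit (except for visits less than 24 hours from the last visit"). Section 7.3 lists it at T2, T3, T4, T6, T8 and T9.

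Section 5.7.1 says an investigator may terminate participation if "The participant meets an exclusion criterion (either newly developed or not previously recognized) that precludes further study participation". On what follows, Section 5.7.2 says: "Every effort will be made to undertake the protocol-specified safety follow-up procedures to capture AEs, SAEs, and UPs". It sets safety or survival data as the minimum for those lost to follow-up, rules out replacement, and leaves partial data to the SAP. For pregnancy, by contrast, Section 15.4 says "administration of study medication will be discontinued, but all other follow-up data, including safety data, will be collected".

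On analysis, Section 20.3.2 places the primary contrast for drinks per day and for PCL-5 at week 6 (T8). Section 6.1.9 admits to the primary analyses only those who complete treatment through T8. Section 20.3.1 bases efficacy on an ITT population: at least one dose and at least one on-drug post-baseline efficacy measurement.

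On THC, Section 2.3 says "THC levels will be obtained from CBD-treated participants to determine whether CBD metabolites are converted into THC". Hypothesis 1a in Section 20.2 predicts no treatment-associated rise in plasma THC.

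**The concern.** An eligibility criterion should act before randomisation. Criterion 17 also acts at treatment visits, and the plan does not separate two decisions: whether the participant goes on taking study drug, and whether the trial goes on measuring the participant. If participation ends, nothing commits the site to further Timeline Followback or PCL-5 data, so the value that carries each efficacy contrast may never be obtained. The people affected are chosen by a result observed after randomisation, and comparability of the arms is then no longer protected by the randomisation.

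The THC clause adds a narrower worry. The protocol treats conversion of CBD to THC as an open question. If conversion happened and were enough to turn a urine screen positive, those particular positives could arise only in the CBD arm. Ending participation would then select on a consequence of treatment and would lose the later plasma THC samples of the participants concerned.

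**Working it through.** The plan gives no figure on this point to reproduce. The check has four parts.

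**1. Which data are at risk.** Section 7.1.7 takes PCL-5 at baseline and weeks 2, 4, 6 and 7. Section 7.3 records alcohol use at T2, T3, T4, T6, T8, T9 and T10. Suppose the flagged visit is completed and nothing is collected afterwards:

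- Positive at T3 (week 1): drinking data to week 1; no post-baseline PCL-5.
- Positive at T4 (week 2): drinking data and PCL-5 to week 2 only.
- Positive at T6 (week 4): drinking data and PCL-5 to week 4 only.

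In each case week 6 is missing for both endpoints. Under Section 6.1.9 all three participants leave the primary analyses. Under Section 20.3.1 all three stay in the ITT population, because they have on-drug drinking data. The MMRM then uses their earlier visits, but the one flagged at T3 has no PCL-5 change score to contribute.

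**2. How many.** Assume a chance p of a positive for any of the three drug classes at each screen, independent across the k = 3 screens at T3, T4 and T6. A positive at T8 is too late to cost the T8 data.

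P(at least one positive) = 1 − (1 − p)^k

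- p = 2%: 1 − 0.98³ = 0.0588, and 0.0588 × 48 = 2.8 participants.
- p = 5%: 1 − 0.95³ = 0.1426, and 0.1426 × 48 = 6.8 participants.

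T2 is left out because Section 7.1 exempts the 1-day visit, although Section 7.3 lists urine there. With T2 included (k = 4) the figures are 1 − 0.98⁴ = 0.0776 (3.7 of 48) and 1 − 0.95⁴ = 0.1855 (8.9 of 48).

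These are counts of participants with a positive. They bound removals from above, since not every positive need lead to removal.

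**3. What it could do to a completers contrast.** If a fraction f of an arm is removed and the mean outcome of those removed differs by m SD from that of those retained, the retained mean differs from the full-arm mean by f × m. The effect on the between-arm contrast is f₁m₁ − f₀m₀, which is zero if both arms are affected alike. Take the extreme case of removals in the CBD arm only, with m assumed between 0.25 and 1.0 SD:

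- 0.0588 × 0.25 = 0.015 SD
- 0.1426 × 1.0 = 0.14 SD

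The loss of power is small. For a two-sided t test at 0.05 with 30 and 18 participants, the effect size giving 80% power is 0.853. The same fractions of 30 are 0.0588 × 30 = 1.8 and 0.1426 × 30 = 4.3 participants. Removing 2 or 4 from the CBD arm raises that effect size to 0.865 or 0.879. (Section 20.4 states 0.939, which matches 25 and 15 rather than 30 and 18. That is a separate matter, and nothing here depends on it.)

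**4. Plasma THC.** Conversion is assessed in plasma by LC-MS/MS (Section 7.1.1), not by the urine screen. Plasma is scheduled at T1 and T2 and at the same T3, T4, T6 and T8 visits as the urine. A participant flagged at T4, for example, has samples scheduled up to and including T4 and would lose T6, T8 and T9.

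**The case against.** Removal is not automatic. Section 5.7.1 says the investigator may terminate. For THC and cocaine, criterion 17 says "their enrollment will be subject to the clinical judgement of the Principal Investigator"; only the opioid sentence reads as mandatory, and it too works through the permissive 5.7.1. The Safety SOP that the criterion cites is not among the documents and may say what happens after a later positive. The formal SAP is still to be written (Section 20.1), the ITT and MMRM text would use partial data, and Section 20.3.5 tallies reasons for discontinuation, so exits under this rule could be identified. Screening for drugs during treatment also has a legitimate safety purpose.

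All of this stands, and it limits how often data would be lost. It does not supply the missing commitment: neither an SAP nor an MMRM can restore a week-6 value that was not collected, and 6.1.9 still contradicts 20.3.1.

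Several stronger readings are tempting, but the documents do not support them:

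- **The THC rule acts only on the CBD arm.** It applies to anyone with a positive, including a placebo participant who uses cannabis despite inclusion criterion 9. Only positives caused by conversion would be confined to CBD. The plan predicts no THC rise and does not say whether conversion would register on a urine screen.
- **Removal hides the conversion signal.** Samples at and before the flagged visit are scheduled; only later ones would be lost.
- **The 90% follow-up figure in Section 5.4 is an allowance for losses.** It is a trigger for reviewing tracking procedures and cannot serve as a benchmark here.

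**Conclusion.** The point holds as a gap in the data-collection rules. An eligibility criterion is applied at treatment visits, participation may be ended because of it, and only safety follow-up is then promised. Week-6 drinks per day and PCL-5 may therefore be missing for some randomised participants, and two sections disagree on whether those participants belong in the primary analyses.

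The size is not known. Under the assumed 2% to 5% per screen, independent over T3, T4 and T6, at most 5.9% to 14.3% (2.8 to 6.8 of 48) would be removed. A reader might infer that the week-6 contrasts are biased. The documents do not establish that: it would require removals, or the outcomes of those removed, to differ between arms. The possible arm difference through THC rests on two undocumented steps (conversion, and a positive urine screen because of it) followed by a discretionary decision. Selection is the main issue, more than power. The point is worth acting on because the remedy is cheap and uncollected data cannot be recovered later.

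**What to change.** Reconcile criterion 17 with Sections 5.7.1 and 5.7.2, stating in 5.2 and 5.7 that:

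1. criterion 17 determines eligibility before randomisation;
2. a positive screen after randomisation is recorded and reported by arm;
3. any decision about study drug after such a result is a separate clinical matter under the Safety SOP, on which this point takes no position;
4. all scheduled efficacy and safety assessments continue through T9/T10 for every randomised participant who does not withdraw consent, in line with what 15.4 already provides for pregnancy.

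Reconcile Section 6.1.9 with Section 20.3.1, so that the primary analysis population is defined once and the handling of these participants is fixed before unblinding.

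The cost is protocol wording, and a few participants attending visits that are already scheduled.

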# 7.2 Laboratory and Voice-markers Procedures/Evaluations

Plasma will be collected at baseline before treatment, and 45 minutes, 1 day, 1 week, 2 weeks, 4 weeks 6 weeks, and 7 weeks after the first dose of treatment with CBD or placebo. CBD, THC and THC metabolite levels will be obtained from the CBD group only. Anandamide levels will be obtained from both the CBD and placebo groups. Serum will be collected at baseline, at 4 weeks, and at 6 weeks for measurement of CDT.

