## 20.2 Statistical Hypotheses

Hypothesis 1a Safety and tolerability: CBD will be safe and well tolerated and will not lead to increased plasma THC. No clinically significant cognitive or motoric impairments, CBD-related serious adverse events, persisting adverse effects or treatment associated increases in plasma THC will be observed.

Hypothesis 1b: Alcohol use. Relative to the placebo-treated group, CBD-treated participants will have fewer drinks per day during the 6 weeks of treatment with CBD vs placebo.

Hypothesis 2: PTSD symptoms. Relative to the placebo-treated group, CBD-treated participants will lower PTSD symptoms during the 6 weeks of treatment with CBD vsplacebo.

Hypothesis 3a: Mechanism, traumatic stress-induced craving: Relative to placebo, CBD will be associated with a greater reduction between baseline and end of treatment in trauma induced alcohol craving, negative emotion, and psychophysiological arousal in response to the task.

Hypothesis 3b: Mechanism, AUD and PTSD related measures and cognition: Relative to placebo, CBD will improve self-report measures of craving, anxiety, mood, self-efficacy and cognitive performance.

Hypothesis 3c: Mechanism, anandamide: Relative to placebo, CBD will be associated with a greater increase

Hypothesis 4: CBD plasma levels. Within-group plasma CBD levels will stabilize within one week, i.e. 45 minutes post-CBD dosing levels obtained after 1 week of treatment will not differ from those obtained after 4 weeks of treatment at each dose.

Exploratory Hypothesis 1: Relationship between effects on PTSD symptoms and alcohol use. The onset of reduction in PTSD symptoms will precede the onset of reduction in alcohol use.

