#### 20.3.4 Safety Analyses

Means and standard deviations of plasma CBD and THC levels within the CBD treatment group will be presented following 45 minutes (T1), 1 day (T2), 1 week (T3), 2 weeks (T4), 4 weeks (T6),6 weeks (T8) of treatment with CBD vs. placebo, and one week (T9) after the completion of treatment to determine whether target plasma levels of CBD have been achieved, and whether metabolic transformation of CBD to THC has occurred.

The number of participants within each treatment group that were able to pass a battery of psychomotor field sobriety tasks (walk-and-turn task, one-leg stand, Romberg's test, finger-finger test, and counting backwards

[85]) within 2 hours of the initial administration of CBD vs. placebo (T1) will be analyzed as summary statistics during treatment.

AEs and SAEs, when present, will be collected on an AE Case Report Form at study visits. The form will include an assessment of clinical significance and study relatedness. Serious Adverse Events (SAEs) will be documented on an additional SAE form. These CRFs will be based on those used in recent NIDA Clinical Trials Network trials. To further assess abuse potential, visual analog scales will be used to assess abuse potential. Scales will include desire to use the study medication again, desire to use the study medication again for pleasurable intoxication ("to get high"), and craving for the study medication.

The study may be stopped if there are untoward and concerning levels of Adverse Event (AE) or Serious Adverse Event (SAE) outcomes attributable to CBD or study participation. If the DSMB finds it is likely that CBD is contributing to negative outcomes, they will consider solutions including protocol changes or potentially stopping the study.

The frequency of adverse events will be analyzed for the entire sample tabulated for each treatment group and compared using chi-squared tests. The safety analysis will be largely descriptive of outcomes for the entire study population. The incidence of AEs will be summarized by system organ class, preferred term, the likelihood of its relationship to the treatment, and severity for each treatment group. Clinical laboratory data will be summarized by type of test. Frequency and percentage of patients whose values fall outside of reference ranges will be presented for each measurement.

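### CBD-to-THC conversion is judged from CBD-arm mean plasma THC, although THC-positive people may enter and stay and no analysis rule separates outside cannabis from conversion

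*Combined protocol and SAP*

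**What the plan says.** **The question.** Conversion is a declared safety question. Section 2.3 gives the purpose: "THC levels will be obtained from CBD-treated participants to determine whether CBD metabolites are converted into THC". Hypothesis 1a in section 20.2 predicts that "CBD will be safe and well tolerated and will not lead to increased plasma THC".

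**The analysis.** Section 20.3.4 presents means and SDs of plasma THC within the CBD arm at T1, T2, T3, T4, T6, T8 and T9, to determine among other things "whether metabolic transformation of CBD to THC has occurred". Section 20.3.3 (Hypothesis 4) sends THC through the anandamide method, with within- and between-group comparisons at the same visits. Section 7.2 states that "CBD, THC and THC metabolite levels will be obtained from the CBD group only".

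**Who may enter and stay.** Inclusion 9 requires agreement to abstain from other cannabinoids. Exclusion 8 bars even mild current cannabis use disorder. Exclusion 12 bars "Current use of exclusionary medications, including cannabinoids". Exclusion 17 makes an opioid-positive screen a flat exclusion, but leaves a THC-positive one to the principal investigator's judgement, in a sentence beginning "If a participant has a positive drug screen for THC or cocaine at screen, baseline or a later visit- their enrollment will be subject to". It also refers to a safety SOP that is not among the documents. Section 7.5 prohibits cannabinoids during the study unless the principal investigator approves.

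**Possible removal.** Section 5.7.1 says an investigator may end participation on this ground: "The participant meets an exclusion criterion (either newly developed or not previously recognized) that precludes further study participation".

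**The concern.** The statistic used to decide whether conversion occurred does not distinguish THC formed from CBD from THC taken in as cannabis. Two errors can follow, in opposite directions:

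- A participant who uses cannabis during treatment adds THC to the later-visit means, which looks like conversion.
- A participant who enters with THC on board and then abstains contributes falling values, which can offset a real rise.

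With no placebo THC values, nothing in the planned data shows the background level of outside exposure. At stake is the THC part of Hypothesis 1a, the claim that no "treatment associated increases in plasma THC will be observed". The drinking and PCL-5 results are not affected by this point.

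**Working it through.** The plan gives no figure on this point to reproduce. The check is a reading of the text followed by illustrations under stated assumptions.

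**Step 1: is outside exposure controlled at any comparison?**

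| Comparison | What the plan provides | Outside cannabis controlled? |
|---|---|---|
| Against placebo | THC assayed in the CBD arm only (7.2) | No |
| B1 to T1 | Pre-dose plasma at B1 (7.3.2); plasma 45 minutes after the first dose; participant kept on site about 2 hours (6.3.1) | Largely, but covers the first dose only |
| B1 to later visits | B1 plasma collected but not named in the THC analyses of 20.3.3 or 20.3.4 | Entry exposure could be handled; use during treatment could not |
| By urine screen | Screens at in-person visits, to check for recent drug use (7.1) | Recorded, but no rule links them to the THC analysis |

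The statistical summary in the Protocol Summary does name baseline, but for plasma CBD.

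**Step 2: how far can outside users move the arm mean?** The planned CBD arm is n = 30 (section 20.5.1). Assume k users with plasma THC of c ng/mL and 30 − k participants at 0. Then mean = kc/30 and SD = √[(kc² − 30·mean²)/29]. The values of c are assumptions; the documents give none.

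| k | c = 1 ng/mL: mean (SD) | c = 5 ng/mL: mean (SD) |
|---|---|---|
| 1 | 0.033 (0.18) | 0.167 (0.91) |
| 3 | 0.10 (0.31) | 0.50 (1.53) |

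Every entry arises with no conversion at all. In the other direction, if three users at 5 ng/mL enter and then abstain, the mean falls from 0.50 to 0, so true conversion adding 0.50 ng/mL on average would leave a flat curve. At 1 ng/mL the masked amount is 0.10.

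**Step 3: how likely is at least one outside user?** With an assumed rate q, the chance is 1 − (1 − q)³⁰: 0.79 for q = 5%, 0.96 for 10%, and above 0.99 for 20%. The expected numbers are 1.5, 3 and 6.

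**Step 4: what could removal after a later positive screen do?** Suppose a share p of the CBD arm truly converts and turns the screen positive, there is no outside use, and a fraction r of positives is removed and dropped from the analysis. The share seen among those retained is p(1 − r)/(1 − pr).

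- p = 10%, r = 0.5: 0.05/0.95 = 5.3%.
- p = 20%, r = 0.5: 0.10/0.90 = 11.1%.
- r = 1: 0 in either case.

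This is conditional on conversion being detectable in urine, on the investigator acting, and on the data being dropped. The documents give no screen cutoff and no removal rate, so neither p nor r can be estimated.

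**Step 5: would removal lose the plasma?** The visit lists in 7.3.3 put urine screen and THC plasma at the same visit at T2, T3, T4, T6, T8 and T9 (section 7.1 exempts the one-day visit from the screen). Plasma from the visit of a first positive can therefore be in hand. The safety analysis is described for the whole study population (20.3.4), and section 5.7.2 sends partial data to the SAP. The completer restriction in 6.1.9 concerns the primary statistical analyses. No section says which of these governs plasma THC.

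**The case against.** The safeguards are real. Cannabis use disorder is excluded, participants agree to abstain, and urine screens recur. The B1-to-T1 pair is taken under observation. The safety analysis is mainly descriptive. A formal SAP is still to be written (20.1), and the safety SOP cited in item 17 may add handling rules. All of this stands and limits the size of the problem. It does not supply an analysis rule for entry-positive participants or for outside use at later visits.

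Three stronger readings are tempting, and the documents do not support them:

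- **The plan removes converters and so is biased toward finding no conversion.** Item 17 leaves a THC-positive result to judgement, and 5.7.1 permits termination without requiring it. Conversion would also have to turn the screen positive, which cannot be checked. Positives from outside cannabis can arise in both arms, and under 20.5.1 assignment is known only to a designated unblinded staff member. This is a risk of unknown size.
- **No THC result can be attributed to CBD.** New outside use between B1 and T1 is very unlikely, so that comparison remains informative even in someone positive at entry.
- **Items 12 and 17 contradict each other.** Item 12 concerns current use; item 17 concerns a positive screen, which section 7.1 treats as a sign of recent use. They need to be read together and reconciled, but they are not plainly incompatible.

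**Conclusion.** The point holds in a limited form. THC-positive people may enter and remain at the investigator's discretion, while conversion is to be judged from CBD-arm means and SDs that do not name the B1 sample and have no concurrent THC control. Later-visit means can be raised by outside cannabis, or a rise can be masked by clearance of THC present at entry. The two effects oppose each other, so the net direction is unknown.

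The illustrated shift of 0.10 to 0.50 ng/mL rests on three users out of 30, an assumed 1 to 5 ng/mL, and zero in everyone else. It shows that the chosen statistic is sensitive to a few people, not that contamination will occur. Loss of possible converters is a risk and has not been demonstrated.

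This is a cheap improvement to one part of the safety hypothesis. It lies between something to consider and something that should be done.

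**What to change.** In section 20.3.4, or in the formal SAP before unblinding:

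1. Base the conversion analysis on CBD participants with THC-negative urine at screening and B1 and no quantifiable THC or THC metabolites in B1 plasma. List the others separately. State the limit of quantification.
2. Report within-person change from B1, including B1 to T1, and the number and proportion with newly quantifiable THC or metabolites. Set these beside the serial urine results and any cannabis use recorded, and do not rely on arm means alone.
3. Keep every plasma THC result already collected in this analysis, including the visit of a first positive screen, whether or not the participant continues.

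Inclusion 9, exclusions 12 and 17, and sections 5.7.1 and 7.5 should be reconciled on cannabinoid exposure. The clinical rule itself is for the investigators.

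**Cost.** Wording only; the samples and screens are already planned. The set is slightly smaller: if no one shows new THC, the upper limit of the two-sided 95% exact interval, 1 − 0.025^(1/n), is 11.6% with n = 30 and 12.8% with n = 27.

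**What remains.** Outside use during treatment is still not fully controlled. No visit list after screening explicitly schedules a cannabis-use self-report, so recorded use may be incomplete. Assaying THC in the placebo plasma already drawn for anandamide would give a concurrent control at extra laboratory cost. That is a separate decision.
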